### **5.1.2.5 Treatment Beyond Progression**

Tumor progression and response endpoints will be assessed using RECIST v1.1 criteria for solid tumors ([Appendix 5](#)) or per PCWG 3 criteria for prostate ([Appendix 12](#)). Treatment beyond progression may be allowed in selected participants with initial RECIST v1.1/PCWG 3-defined progressive disease following discussion and agreement with the BMS Medical Monitor (or designee), if the benefit-risk assessment favors continued administration of study treatment (eg, participants are continuing to experience clinical benefit as assessed by the Investigator, tolerating treatment, and meeting other criteria, see [Section 8.1.1](#)).

### **5.1.3     Follow-up**

#### **5.1.3.1    Safety Follow-up Period**

Upon completion of study therapy (up to a maximum of 2 calendar years for BMS-986218 Q4W ± nivolumab Q4W; up to a maximum of 2 calendar years for BMS-986218 Q2W; up to a maximum of 4 doses for ipilimumab Q3W), or once the decision is made to discontinue the participant from treatment (ie, at end of treatment [EOT]), all participants will enter the Safety Follow-up Period.

For participants who complete all scheduled cycles of therapy, the EOT visit will be the same visit as the last scheduled and completed on-treatment visit and will be the start of the Safety Follow-up Period. For participants who do not complete all scheduled cycles of therapy, the EOT visit will be the most recent on-treatment visit (with all available safety and response data) and will not need to be repeated. Accordingly, for these participants, this visit will be considered the start of the Safety Follow-up Period.

After the EOT visit, all participants will be evaluated for any new AEs for at least 100 days after the last dose of study treatment. Follow-up visits should occur at Days 30, 60, and 100 ( $\pm$  7 days for all study visits) after the last dose, or the date of discontinuation ( $\pm$  7 days). All participants will be required to complete the 3 clinical Safety Follow-up visits, regardless of whether new anti-cancer therapy is started, except those participants who withdraw consent for study participation.

#### **5.1.3.2    Response Follow-up Period**

At the time of the EOT visit or at the time of study treatment discontinuation, all participants will continue to have radiologic and clinical tumor assessments Q8W ( $\pm$  1 week) until subsequent tumor-directed therapy is initiated. Participants who remain free of subsequent therapy will continue to receive tumor assessment scans Q8W for the first 48 weeks after discontinuation of study treatment/EOT visit and then Q12W ( $\pm$  2 weeks) for a total duration of 2 years. Subsequently, they will continue to receive tumor assessment scans as per standard of care guidelines, or at a minimum of every 6 months up to 2 years following the last dose of study treatment, or until new tumor-directed therapy initiation/withdrawal of study consent. Radiologic assessments for participants who have ongoing clinical benefit may continue to be collected after participants complete the survival follow up period of the study. Scans will be submitted to an imaging core laboratory for review by blinded independent central review (BICR) at a later date or at any time during the study at the Sponsor's discretion.

#### **5.1.3.3    Survival Follow-up Period**

In parallel with the Safety Follow-up Period, all participants will start the Survival Follow-up Period. Participants will be followed-up by telephone Q12W ( $\pm$  2 weeks) from EOT for up to 4 years following the first dose of study treatment or until death, loss to follow-up, withdrawal of consent, or conclusion of the study, whichever comes first. [REDACTED]

[REDACTED] Participants with stable disease (SD), partial response (PR), or complete response (CR) will have both the Response Follow-up period and Survival Follow-up

Period occur simultaneously during the 2-year follow-up period. The duration of this follow-up is up to 4 years following the first dose of study treatment, although a longer follow-up period could be considered in selected cases if an efficacy signal is apparent. Tumor assessment scans, for participants who have ongoing clinical benefit beyond the 4-year period following the first dose of study treatment, may continue to be collected as part of standard-of-care treatment. Subsequent therapies will also be recorded in this Survival Follow-up Period.

#### **5.1.4 Data Monitoring Committee and Other External Committees**

Based upon the stage of the study and appropriate safety monitoring procedures described below, BMS has determined that a Data Monitoring Committee is not necessary for this study.

BMS has developed a multi-layered process to ensure safety monitoring through close collaboration of study site Investigators, the BMS study team, and the BMS WorldWide Patient Safety (WWPS) led Safety Management Team (SMT). This collaborative process constitutes the safety monitoring plan for the study. To support safety oversight, BMS has established ongoing processes for collection, review, analysis, and submission of individual adverse event reports and their aggregate analyses. Because this is an open-label study, WWPS, the BMS Medical Monitor, and the Investigators will have access to all data necessary for safety evaluation.

BMS WWPS is an internal group that operates independently from the clinical team to monitor safety across all BMS protocols and analyze all data in an unblinded fashion. Within BMS, an SMT is established for investigational therapies under clinical development, and a member of WWPS chairs this team. In addition, signal detection is performed at least monthly and ad hoc throughout the study by the SMT composed, at a minimum, of the WWPS medical safety assessment physician (Chair of the SMT) and WWPS single case review physician, the Clinical Development Lead, the study biostatistician, and epidemiologist; all of whom, analyze the data in an unblinded fashion. Furthermore, the SMT routinely monitors for actual or potential issues related to participant safety that could result in a change in the medical risk-benefit balance associated with the use of study treatment(s).

All participants in this study represent individuals with high unmet medical need as the prognosis for advanced/metastatic solid tumors is generally very poor.

#### **5.2 Number of Participants**

The approximate total number of evaluable participants will be up to 684 as shown below:

- Part 1 - Dose Escalation Phase: Up to approximately 284 evaluable participants may be treated in the escalation phase including:
  - Part 1A - up to approximately 200 evaluable participants for the BMS-986218 Monotherapy Escalation
    - Part 1A Q4W monotherapy - up to approximately 108 DLT-evaluable participants will be treated.
    - Part 1A Q2W monotherapy - up to approximately 72 DLT-evaluable participants will be treated.

- Part 1A PD cohort - approximately 20 evaluable participants will be treated in the Part 1 PD cohorts.
  - In addition, in order to evaluate more than one dose level or schedule, up to 40 additional evaluable participants may be treated in the Part 1A PD cohorts (from participants initially planned for other Part 1 cohorts), provided the total number of participants in Part 1 is not exceeded.
- Part 1B - up to approximately 84 DLT-evaluable participants for the Safety Evaluation of Combination Doses of BMS-986218 with Nivolumab.
- Part 2 - Dose Expansion Phase: The remaining 400 response-evaluable participants represent the potential number of participants in BMS-986218 cohort expansions who may be either randomized (Part 2A and Part 2B) or treated (Part 2C and Part 2D) including:
  - Part 2A - for the Randomized BMS-986218 Monotherapy Cohort Expansion in Cutaneous Melanoma, approximately 132 evaluable participants will be randomized, with 33 evaluable participants per arm required.
  - Part 2B - for the BMS-986218 Monotherapy Cohort Expansion in NSCLC, approximately 66 evaluable participants will be randomized, with 22 evaluable participants per arm required.
  - In Part 2A and Part 2B, additional participants may be treated or randomized to further evaluate emerging data or subgroups of interest if needed but not to exceed a total of 40 evaluable participants per arm. If additional participants are treated or randomized in Part 2A and Part 2B, then up to 160 response-evaluable participants (= 40 participants  $\times$  4 arms) and 120 response-evaluable participants (= 40 participants  $\times$  3 arms) can be randomized in Part 2A and Part 2B, respectively.
  - Part 2C - for the BMS-986218 Combination Therapy Cohort Expansion in NSCLC, approximately 40 response-evaluable participants will be treated. If more than one dose level is evaluated, additional participants (up to 40 response-evaluable participants per dose level) may be enrolled, up to 80 response-evaluable participants (= 40 participants  $\times$  2 arms).
  - Part 2D - for the BMS 986218 Combination Therapy Cohort Expansion in MSS CRC, approximately 40 response-evaluable participants will be treated, with the goal of treating approximately 20 participants each with either mutation or wild-type with respect to extended RAS status.

For additional details on sample size determination, see [Section 10.1](#).

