### 7.4 Method of Treatment Assignment

During the screening visit, the investigative site will call into the enrollment option of the IRT designated by BMS for assignment of a 5-digit participant number that will be unique across all sites. Enrolled participants, including those not dosed, will be assigned sequential participant numbers [REDACTED]. The patient identification number

(PID) will ultimately be comprised of the site number and participant number. For example, the first participant screened (ie, enrolled) at site number 1, will have a PID of [REDACTED]. Once it is determined that the participant meets the eligibility criteria following the screening visit, the investigative site will call the IRT to centrally assign the participant into the open dose panel. If Part 1 is open upon the decision to initiate Part 2, treatment in the 2 parts will occur in parallel.

In the Randomized BMS-986218 Monotherapy Cohort Expansion in Cutaneous Melanoma (Part 2A), all participants will be centrally randomized evenly across study arms, which will include: BMS-986218 monotherapy at 7 mg, 20 mg, 70 mg Q4W or ipilimumab 3 mg/kg Q3W (maximum of 4 doses).

In the Randomized BMS-986218 Monotherapy Cohort Expansion (Part 2B), participants will be randomized evenly across study arms, which will include: BMS-986218 at 7 mg, 20 mg, and 70 mg Q4W.

In Part 2A and Part 2B, if it is decided based on a preliminary assessment of anti-tumor activity that not all arms would need to continue enrollment, randomization would continue only in the arm(s) that remain open. In addition, more subjects may be enrolled in selected arm(s) as specified in [Section 5.2](#) to better assess an initial signal.

In Part 2C Combination Expansion, multiple doses may be open concurrently. In that case, treatment assignments will alternate between the dose levels, with consecutively treated participants assigned to different parts through IRT whenever possible. If there are no openings available in the dose level to which the participant would be assigned by this algorithm, then the subject will be assigned to the next open dose.

In Part 2D Combination Expansion, participants will be assigned to one dose.

In Part 2, BMS-986218 Q4W will be administered for a maximum duration of 2 calendar years, and ipilimumab Q3W will be administered for a maximum of 4 doses.

For Part 2, participant replacement will not be allowed for participants who are discontinued after dosing.

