#### **10.1.5    *The BMS-986218 Combination-Therapy Cohort Expansion in NSCLC (Part 2C)***

The purpose of the BMS-986218 Cohort Expansion - Combination Therapy (Part 2C) is to gather additional data including safety, tolerability, preliminary efficacy as combination therapy of BMS-986218 with nivolumab, in NSCLC. The sample size calculation will be based on the ORR.

Approximately 40 response-evaluable participants will be treated. Initial evaluation of efficacy signal (ORR) will be based on approximately the first 20 response-evaluable participants at a dose level, will be descriptive based on a point estimate and an 80% Clopper Pearson CI for ORR. In order for an 80% CI to exclude a 5.5% ORR (as reported for ipilimumab with nivolumab in similar population), at least 3 responders (15% ORR) will need to be observed in the first 20 participants evaluated at this dose. If 4 responders are observed (20% ORR), the 80% confidence interval will equal (9.0%, 36.1%). Based on the results of this initial evaluation, additional participants for a total of up to 40 participants may be treated at a dose level.

Furthermore, if 40 participants are evaluated at a dose level, there will be approximately 80% power to detect a difference between the null hypothesis assuming ORR of 5.5% and the alternative assuming ORR of 15%, based on a one group  $\chi^2$  test with a 0.10 one-sided significance alpha level. If more than one dose level is evaluated, up to 80 response-evaluable participants (= 40 participants  $\times$  2 arms) may be treated.

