**Table 10.3.1-1: Efficacy - Statistical Analyses**

Endpoint	Statistical Analysis Methods
ORR is defined as the proportion of all treated participants whose BOR is either CR or PR by Investigator per RECIST v1.1 or per PCWG 3 criteria for prostate.  BOR for a participant will be assessed per RECIST v1.1 by Investigator, unless otherwise specified.	Estimate of ORR and corresponding 2-sided exact 95% CI using the Clopper-Pearson method by treatment for each tumor type.  For part 2A, estimate of difference in ORR between arms (using ipilimumab as reference) and corresponding 2-sided exact 95% CI using the Clopper-Pearson method by BMS treatment arms.
Median DOR  DOR for a participant with a BOR of CR or PR is defined as the time between the date of first response and the date of the first objectively documented tumor progression per RECIST v1.1 or per PCWG 3 criteria for prostate, or death, whichever occurs first.	Estimate by the Kaplan-Meier method and corresponding 2-sided 95% CI using Brookmeyer and Crowley methodology (using log-log transformation) by treatment for each tumor type.
PFSR at 24, 36, and 48 weeks  PFS for a participant is defined as the time from the first dosing date to the date of first objectively documented disease progression or death due to any cause, whichever occurs first.	Estimate PFSR by the Kaplan-Meier method and corresponding 2-sided 95% CI using Greenwood formula by treatment for each tumor type.  For part 2A, estimate difference in PFSR between arms (using ipilimumab as reference) by the Kaplan-Meier method and corresponding 2-sided 95% CI using Greenwood formula by BMS treatment arms.  Estimate median PFS by the Kaplan-Meier method and corresponding 2-sided 95% CI using Greenwood formula by treatment for each tumor type.

Abbreviations: BOR = best overall response; BMS = Bristol Myers Squibb; CI = confidence interval; CR = complete response; DOR = duration of response; ORR = objective response rate; PCWG 3 = Prostate Cancer Working Group; PFSR = progression-free survival rate; PR = partial response; RECIST = Response Evaluation Criteria in Solid Tumors.

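### In Parts 2A, 2B and 2C, an arm enlarged because of early activity has an upward-biased pooled ORR, and the plan reports no estimate free of that selection

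*Combined protocol and SAP*

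**What the plan says.** Initial sizes and caps are in Section 5.2. For Part 2A, "approximately 132 evaluable participants will be randomized, with 33 evaluable participants per arm required"; for Part 2B, "approximately 66 evaluable participants will be randomized, with 22 evaluable participants per arm required". Either part may then add participants, "not to exceed a total of 40 evaluable participants per arm". The stated reason is broad: "additional participants may be treated or randomized to further evaluate emerging data or subgroups of interest if needed".

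The link to observed activity is made elsewhere:

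- **Section 7.4 (Parts 2A and 2B).** After a preliminary look at anti-tumor activity, randomization may continue only in the arms left open. In addition, "more subjects may be enrolled in selected arm(s) as specified in" Section 5.2, in order to assess an initial signal better.
- **Section 10.1.5 (Part 2C).** The first 20 or so response-evaluable participants at a dose level are assessed descriptively. Then: "Based on the results of this initial evaluation, additional participants for a total of up to 40 participants may be treated at a dose level". Section 5.1 describes the same step.
- **Section 10.3.9.** Any Part 2 cohort may close if the signal is inadequate. Enrollment may or may not pause for the look.

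Section 10.3.1 bases the final efficacy analysis on all randomized participants (2A, 2B) or all treated participants (2C). Table 10.3.1-1 gives the method: "Estimate of ORR and corresponding 2-sided exact 95% CI using the Clopper-Pearson method by treatment for each tumor type". The plan has no breakdown by stage and no selection-adjusted estimate. The statistical analysis plan is still to be finalized (Section 10.3).

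**The concern.** When an arm grows because its first participants responded well, those participants are a favourably selected group. Keeping them in the final estimate carries part of their good luck forward, and a fixed-size binomial analysis does not allow for that. ORR is a primary efficacy endpoint for Part 2, and the enlarged arms are those in which the plan wants a signal assessed better. A reader who takes the pooled ORR of such an arm at face value would expect too much of it, most of all when the true rate is near the 5.5% benchmark of Section 10.1.5. Participants added to study a subgroup also change the case mix of the pooled arm.

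**Working it through.** **Inputs.** Part 2C: 20, then up to 40; benchmark 5.5%; 3 of 20 as the count whose 80% interval excludes it (Section 10.1.5). Part 2B: 22 to 40. Part 2A: 33 to 40 (Section 5.2). Assumed here: the enlargement triggers, and the same true ORR in early and later participants.

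**The plan's own figures.** The 80% Clopper-Pearson limits for x of n are the 10% quantile of Beta(x, n−x+1) and the 90% quantile of Beta(x+1, n−x). For 4 of 20 this gives (9.02%, 36.07%), matching the stated (9.0%, 36.1%). The lower limit is 5.64% for 3 of 20 and 2.69% for 2 of 20, so 3 is indeed the smallest count that excludes 5.5%.

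**Part 2C, enlarging at 3 or more of 20.** With X ~ Bin(20, p), the mean pooled ORR given enlargement is (E[X | X ≥ 3] + 20p) / 40.

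| True p | P(X ≥ 3) | E[X given X ≥ 3] | First-20 ORR | Pooled ORR | Bias (points) |
|---|---|---|---|---|---|
| 5.5% | 9.4% | 3.279 | 16.4% | (3.279 + 1.1)/40 = 10.9% | +5.4 |
| 10% | 32.3% | 3.589 | 17.9% | (3.589 + 2)/40 = 14.0% | +4.0 |
| 15% | 59.5% | 4.041 | 20.2% | (4.041 + 3)/40 = 17.6% | +2.6 |

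With triggers from 2 of 20 to 4 of 20, the bias runs from +3.2 to +7.8 points at a true 5.5% and from +1.2 to +4.4 at 15%.

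**Parts 2A and 2B, enlarging only the best of three equal BMS-986218 arms.** With M the largest of three independent Bin(n, p) counts, the mean pooled ORR is (E[M] + (40−n)p) / 40. At a true 10%:

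- Part 2B: E[M] = 3.399, so (3.399 + 1.8)/40 = 13.0%. Without enlargement the best arm would show 3.399/22 = 15.4%.
- Part 2A: E[M] = 4.772, so (4.772 + 0.7)/40 = 13.7%. Without enlargement it would show 4.772/33 = 14.5%.

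Over true rates of 5.5% to 15% the bias is +2.3 to +3.6 points in Part 2B and +2.8 to +4.4 in Part 2A.

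**Interval and error rate, Part 2C, trigger 3 of 20.** Among enlarged arms, the two-sided 95% interval covers the truth 84.0%, 95.5% and 98.0% of the time at true 5.5%, 10% and 15%. At a true 5.5% the misses are all on one side: the lower limit passes 5.5% from 6 of 40 upward (5.71%; 5 of 40 gives 4.19%), which happens in 16.0% of enlarged arms. Since 9.4% of such arms are enlarged, the rate over all arms is 9.4% × 16.0% = 1.5%. For a fixed 40 it is P(S ≥ 6) = 2.1%, with S ~ Bin(40, 5.5%).

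**All arms together.** Averaging enlarged and stopped arms, the mean reported ORR is slightly low: −0.5 point at a true 5.5% and −1.6 at 15%.

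**The case against.** The case on the other side is substantial, and much of it stands.

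- **The triggers are not in the plan.** The Part 2C look is descriptive and its enlargement optional; Parts 2A and 2B have no threshold. Section 5.2 also gives totals with every arm at 40 (160 and 120). If all arms grow whatever their data, there is no selection and no bias. This stands, so the figures are conditional on assumed rules.
- **Section 5.2 does not itself name a response signal.** For Part 2C its extra-participant clause, "additional participants (up to 40 response-evaluable participants per dose level) may be enrolled", depends on more than one dose level being evaluated. The activity link comes from Sections 7.4, 10.1.5 and 10.3.9, where it is explicit.
- **Enlargement reduces the bias.** A reader might infer that adding participants creates it. The calculations show the reverse: in Part 2C at a true 5.5%, the selected first-20 ORR of 16.4% falls to 10.9% once 20 more are added. The cause is the selection.
- **No inflation of error.** A reader might set the 16.0% of enlarged arms against the 2.1% for a fixed 40 and conclude that false signals become more common. That compares a conditional rate with an unconditional one. The matching figure is 1.5%, below 2.1%.
- **Part 2 is exploratory.** Section 3.2.1 says no hypotheses are formally tested, and Section 10.3.9 waives significance adjustment. That answers a concern about alpha. It does not answer one about the estimate reported for a selected arm.

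**Conclusion.** The point holds as one of estimation in selected arms. Given that a Part 2A, 2B or 2C arm or dose level was continued or enlarged on early activity, its pooled ORR is biased upward. The size is about 3 to 5 points in Part 2C at true rates of 5.5% to 15% under a 3-of-20 trigger, and about 2 to 4 points in Parts 2A and 2B if only the best of three equal arms grows. For scale, Section 10.1.3 considers effect sizes of 10 to 20 points.

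Only about 9% of Part 2C dose levels with a true 5.5% would be enlarged under that trigger. Of the three rates checked there, interval coverage falls short only at 5.5%. The documents do not support reading this as an inflated error rate, as harm done by enlargement, or as a defect of Part 2D, whose target of about 40 is not tied to a signal. The remaining gap is that the plan provides no ORR free of the selection. It is worth closing because doing so is cheap.

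**What to change.** Add to Table 10.3.1-1, and carry into the SAP: for any Part 2A, 2B or 2C arm or dose level enrolled beyond its initial size after a look at activity, ORR with its 95% Clopper-Pearson interval is reported separately for participants assigned before and after that decision, beside the pooled ORR. Identify the after-decision ORR as the estimate not affected by the selection. Show participants added to study a subgroup separately. Record the decision date, since Section 10.3.9 allows enrollment to run on without a pause.

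This changes no enrollment, visit or procedure. It costs table and SAP wording and the extra rows for each enlarged arm; assignment already runs through the IRT (Section 7.4). The downside is precision: full enlargement leaves 40 − 33 = 7 after-decision participants in Part 2A, 40 − 22 = 18 in Part 2B and 40 − 20 = 20 in Part 2C, so those intervals will be wide. That is why the pooled ORR should stay beside them.
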